1 PROTOCOL SUMMARY

1.1 SYNOPSIS

Title: Gemcabene for the Treatment of Pediatric NAFLD: A Phase 2a Study
Study Description: This is a multicenter, prospective, open-label, Phase 2, proof of concept study to test preliminary efficacy and safety of gemcabene in children with established NAFLD incompletely treated by lifestyle changes who are ages 12-17 years. The hypothesis of the study is that 300 mg of gemcabene once a day for twelve weeks will reduce ALT, hepatic steatosis, dyslipidemia and down regulate de novo lipogenesis in children with NAFLD.

Objectives:

Primary Objective: To evaluate safety and preliminary efficacy using multiple biomarkers of NAFLD (ALT, AST, GGT, hepatic steatosis) in children aged 12-17 years with established NAFLD not resolved by lifestyle changes.

Secondary Objectives: To assess indices demonstrating drug response and mechanism of action.

Endpoints:

Primary Endpoints:

- Percent change in ALT from Baseline to Week 12

Secondary Endpoints:

- Absolute change in ALT from Baseline to Weeks 6 and 12
- Percent change in ALT from Baseline to Weeks 6
- Percent change in ALT from Baseline to a mean of Week 6 and 12 ALT
- Absolute change and percent change in hepatic steatosis from Baseline to Week 12 as measured by MRI (volumetric fat fraction-HepaFat)
- Absolute change and percent change in pancreatic fat from Baseline to Week 12 as measured by MRI (HepaFat)
- Absolute change and percent change in AST from Baseline to Week 6 and Week 12
- Absolute change and percent change in insulin sensitivity as assessed by fasting insulin, fasting glucose, and HOMA-IR from Baseline to Week 6 and Week 12
- Absolute change and percent change in GGT from Baseline to Week 6 and Week 12
- Absolute change and percent change in serum lipids including total cholesterol, non-HDL-C, HDL-C, VLDL-C, LDL-C, and triglycerides (TG) from Baseline to Week 6 and Week 12
- Absolute change and percent change in apolipoproteins including apoA-1, apoB, apoC-II, apoE and apoCIII
- Absolute change and percent change in inflammatory markers such as hsCRP, IL-1B, IL-6 and procollagen III.
- Absolute change and percent change in lipoprotein particle sizes (VLDL, HDL, LDL, chylomicrons [NMR])
- Absolute change and percent change in post-prandial lipids (total cholesterol, non-HDL-C, HDL-C, VLDL-C, LDL-C, TG, lipoprotein particle size)
- Absolute change and percent change in rate of de novo lipogenesis using stable isotope tracers
- Absolute change and percent change in liver inflammation and fibrosis score (LIF and cT1) by MRI Liver MultiScan.
- Change in body composition measures by AMRA from Baseline to Week 12
- Absolute change and percent change in anthropometric measures including height, weight, body mass index, and waist circumference from Baseline to Week 12
- Safety related endpoints including adverse events (AEs), vital signs, clinical labs, hematology and urinalysis
- Treatment tolerance and compliance

Study Population: 40 enrolled (36 completers) boys and girls, aged 12-17 years, diagnosed with NAFLD

Phase: 2a

[figure not shown]
Sites/Facilities Enrolling Participants: Up to 3 US sites

Study Intervention: 300 mg gemcabene by mouth once a day

Study Duration: 12 months

Participant Duration: 22 weeks

1.2 SCHEMA

1.3 SCHEDULE OF ACTIVITIES (SOA)

Table 1. Schedule of Activities

| | Screening (-6 weeks) | Baseline (Day 1 +/- 2 days) | Week 2 (Day 15+/- 7 days) | Week 6 (Day 43+/- 10 days) | Week 12 (Day 85 +/- 10 days) | Week 16 Follow- up (phone call) Day 113 +/- 10 days | Early Termination Visit | Week 28 Long-Term Follow-up (Month 3) +/- 2 weeks | Week 36 Long-Term Follow-up (Month 6) +/- 2 weeks | Week 60 Long-Term Follow-up (Month 12) +/- 2 weeks |
|--|-------------------------|--------------------------------------|------------------------------------|--|---|---|-------------------------------|---|---|--|
| Informed Consent and HIPAA Authorization | X | | | | | | | | | |
| Review Inclusion/Exclusion Criteria | X | X | | | | | | | | |
| Demographics & Medical History | X | | | | | | | | | |
| Physical Exam | | X | | | X | | X | X | X | X |
| Vital Signs ^A | X | X | X | X | X | | X | X | X | X |
| Standardized lifestyle counseling | | X | | | | | | | | |
| Height, weight, (calculated BMI) waist and hip measurements ^C | X | X | X | X | X | | X | X | X | X |
| Alcohol Use Disorders Identification Test (AUDIT) | X | | | | | | | | | |
| Dietary Assessment (Food Frequency Questionnaire) | | X | | | X | | X | | | |
| MRI | | X | | | X | | X | X | X | X |
| ECG | | X | X | | | | | | | |
| PROMIS Questionnaires (fatigue, depression, anxiety) | | X | | | X | | X | | | |
| Beverage Questionnaire | | X | | | X | | X | | | |
| Tanner Staging (self-administered) | X | | | | | | | | | |
| Physical Activity Assessment (Block) | | X | | | X | | X | | | |
| Local Urine Pregnancy Test (WOCBP) | | X | X | X | X | | X | X | X | X |
| Urinalysis (UA) | X | X | X | X | X | | X | X | X | X |
| Blood Draw ^B | X | X | X | X | X | | X | X | X | X |

| | | | | | | | | | | |
|----------------------------------|---|---|---|---|---|---|---|---|---|---|
| De novo lipogenesis (substudy) | | X | | | X | | | | | |
| Postprandial lipid (substudy) | | X | | | X | | | | | |
| Instructions for Drug Compliance | | X | X | X | | | | | | |
| Drug Dispense | | X | | X | | | | | | |
| Identify clinical follow-up plan | | | | | X | | X | | | |
| Adverse Events Review | | X | X | X | X | X | X | X | X | X |
| Concomitant Medication Review | X | X | X | X | X | X | X | X | X | X |
| Assess Drug Accountability | | | X | X | X | | X | | | |

A – Vital signs to include: temperature, pulse, respirations, and seated blood pressure

B – See details below in Table 2. Blood Draw Schedule

C – Measurements taken in duplicate at each timepoint and a mean will be calculated and recorded

Table 2. Specimen Collection Schedule

| | Screening (-6 weeks) | Baseline (Day 1) | Week 2 (Day 15+/- 7 days) | Week 6 (Day 43+/- 10 days) | Week 12 (Day 85 +/- 10 days) | Early Term Visit | Week 28 Long-term Follow-up (Month 3) | Week 36 Long-term Follow-up (Month 6) | Week 60 Long-term Follow-up (Month 12) |
|--|-------------------------|---------------------|---------------------------------|----------------------------------|------------------------------------|------------------------|--|--|---|
| Local Labs: | | | | | | | | | |
| CMP ^A | X | X | X | X | X | X | X | X | X |
| Creatine phosphokinase (CPK) | X | X | X | X | X | X | X | X | X |
| CBC ^B | X | | | | X | X | X | X | X |
| GGT | X | X | | X | X | X | X | X | X |
| Clinical Lipid Profile ^C | X | | | | | | X | X | X |
| PT/INR | X | X | | X | X | X | X | X | X |
| HbA1c | X | X | | | X | X | X | X | X |
| Urinalysis | X | X | X | X | X | X | X | X | X |
| Central Labs: | | | | | | | | | |
| Plasma & Serum (storage) ^D | X | X | X | X | X | X | X | X | X |
| Urine (storage) ^D | X | X | X | X | X | X | | | |
| Buffy coat for DNA ^D | X | | | | | | | | |
| Fasting lipids ^{E, F} | | X | | X | X | X | | | |
| Fasting apolipoproteins ^{E, G} | | X | | X | X | X | | | |
| Fasting lipoprotein particle sizes ^H | | X | | X | X | X | | | |
| Inflammation (hsCRP) ^E | | X | | X | X | X | | | |
| Liver Function panel ^{E, I} | | X | | X | X | X | | | |
| Diabetes Panel ^{E, J} | | X | | X | X | X | | | |
| Pharmacokinetics | | | X | X | X | X | | | |
| Metabolomics ^D | | X | | | X | X | | | |

A – Comprehensive Metabolic Panel (CMP) includes: Alb, total bilirubin, Ca, CO₂, Cl, Creat, Glu, Alk, Phosphatase, K, TP, Na, ALT, AST, BUN (reflex to direct bilirubin if total bilirubin is elevated)

B – Complete Blood Count (CBC) includes: WBC, RBC, HGB, HCT, MCV, MCH, MCHC, RDW, PLT, neutrophils, lymphs, monocytes, eosinophils, basophils

C – Clinical Lipid Profile includes: cholesterol, triglyceride, HDL, LDL, VLDL

D – Processed locally, shipped to Emory University Biorepository

E – Analyzed by the Cardiovascular Research Lab at the Atlanta VA

F – Fasting lipids includes: TG, CHOL, HDLc, LDLc

G – Fasting apolipoprotein includes: apoA-I, apoB, apoC-II, apoC-III, apoE

H – Analyzed at LabCorp (Liposcience)

I – Liver Function panel includes: ALT, AST

J – Diabetes Panel includes: Glu, INS, NEFA

Note: If the ALT at screening is more than two times the historic value, or there is no historic value available, the subject will be asked to repeat the screening ALT after four weeks. If the repeat ALT is greater than 50% increased or decreased over the screening ALT a third ALT will be obtained.

Table 3. Blood Volume chart

| Number of mLs | Screening (-6 weeks) | Baseline (Day 1) | Week 2 (Day 15 +/- 7 days) | Week 6 (Day 43 +/- 10 days) | Week 12 (Day 85 +/- 10 days) | Week 28 Long-term Follow-up (Month 3) | Week 36 Long-term Follow-up (Month 6) | Week 60 Long-term Follow-up (Month 12) | |
|------------------------------|------------------------------|------------------------------|----------------------------|------------------------------|------------------------------|---------------------------------------|---------------------------------------|--|-----------------|
| Local Labs: | | | | | | | | | TOTAL mL |
| CMP | 8.5 | 8.5 | 8.5 | 8.5 | 8.5 | 8.5 | 8.5 | 8.5 | 68 |
| CPK | inc | inc | inc | inc | inc | inc | inc | inc | - |
| CBC | 4 | - | - | - | 4 | 4 | 4 | 4 | 20 |
| GGT | inc | inc | - | inc | inc | inc | inc | inc | - |
| Clinical Lipid Profile | inc | inc | inc | inc | inc | inc | inc | inc | - |
| PT/INR | 2.7 | 2.7 | - | 2.7 | 2.7 | 2.7 | 2.7 | 2.7 | 18.9 |
| HbA1c | 4 | 4 | - | - | 4 | 4 | 4 | 4 | 24 |
| Safety Lab subtotal | 19.2 | 15.2 | 8.5 | 11.2 | 19.2 | 19.2 | 19.2 | 19.2 | 130.9 |
| Central Labs: | | | | | | | | | |
| Plasma & Serum (storage) | 8 = 4mL Plasma and 4mL Serum | 8 = 4mL Plasma and 4mL Serum | 4 = 4mL Plasma | 8 = 4mL Plasma and 4mL Serum | 8 = 4mL Plasma and 4mL Serum | 4 ml plasma only | 4 ml plasma only | 4 ml plasma only | 48 |
| Central Labs | - | 6 = 6 mL Plasma | - | 6 = 6 mL Plasma | 6 = 6 mL Plasma | - | | | 18 |
| PK | - | - | 3 | 3 | 3 | - | | | 9 |
| Central Lab Subtotals | 8 | 14 | 7 | 17 | 17 | 4 | 4 | 4 | 75 |
| Totals | | | | | | | | | |
| Total w/o substudy | 27.2 | 29.2 | 15.5 | 28.2 | 36.2 | 23.2 | 23.2 | 23.2 | 205.9 |
| PK Substudy | - | - | - | - | 9 | - | - | - | 9 |
| Substudy | - | 56 | - | - | 56 | - | - | - | 112 |
| Total w/ substudy | 27.2 | 85.2 | 15.5 | 28.2 | 101.2 | - | - | - | 327.5 |

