2.2 BACKGROUND

Introduction to Gemcabene: Gemphire Therapeutics Inc. (Gemphire) is developing gemcabene calcium (also denoted as CI-1027 or PD72953 and in this protocol referred to as gemcabene) for multiple indications including:

- 1.) As an adjunct to diet and statin therapy for the treatment of patients with dyslipidemia who require additional low-density lipoprotein cholesterol (LDL-C) lowering such as patients with homozygous familial hypercholesterolemia (HoFH) and heterozygous FH (HeFH) and atherosclerotic cardiovascular disease (ASCVD).
- 2.) To reduce triglycerides (TG) in patients with severe hypertriglyceridemia (TG \geq 500 mg/dL),
- 3.) To reduce or stop progression of hepatic steatosis in patients with nonalcoholic fatty liver disease (NAFLD)/nonalcoholic steatohepatitis (NASH).

To date 18 clinical studies evaluating gemcabene have been conducted (17 completed and 1 terminated for business reasons) evaluating a total of 1278 healthy adult volunteers and participants with 901 exposed to gemcabene providing extensive safety data and preliminary efficacy data for triglyceride reduction. No studies have previously been conducted in NAFLD populations.

Brief Mechanism of Action Summarized from Investigator Brochure Version 2: Gemcabene is the monocalcium salt of a dialkyl ether dicarboxylic acid and is a new class of lipid-regulating compounds because it has 2 terminal gem-dimethyl carboxylate moieties. It has several mechanisms of action including 1) enhancing the clearance of VLDL and 2) blocking the production of hepatic TG and cholesterol synthesis.

The enhanced clearance of VLDL is through decreased apolipoprotein C-III, an apolipoprotein that when elevated can mask apoE on VLDL remnants and inhibit LPL mediated TG lipolysis. Elevated apoC-III is associated with increased CVD risk. Gemcabene decreases apoC-III through decreased expression of mRNA, likely decreasing protein production. This leads to increased VLDL-remnant clearance and enhances LPL activity with the overall effect of lowering LDL-C and TG.

Gemcabene also has effects within the hepatocytes. In primary rat hepatocytes, gemcabene markedly blocked radiolabeled acetate incorporation into both TG and cholesterol. AcetylCoA carboxylase (ACC1) is the rate limiting step in de novo lipogenesis (DNL). Gemcabene may reduce ACC1 mRNA expression as well as inhibit ACC1 enzymatic activity, suggesting that it blocks the ACC1 step during DNL.

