monkeys, over 26 weeks at >30 mg/kg/day fatty changes were seen in the liver and kidneys. Carcinogenicity studies are ongoing in mice and rats. No mutagenic effects were seen in genetic toxicity studies. Developmental toxicity studies demonstrated abnormalities and teratogenicity at doses >10 mg/kg/day in rats but none in rabbits.

Summary of clinical studies with Gemcabene from the Investigator Brochure Version 2:

Phase 1 PK studies have demonstrated that oral gemcabene is rapidly absorbed with exposure increasing approximately linearly with dose. The primary route of elimination is renal. There is no clinically relevant effect on QT interval. There was a rapidly reversible increase in serum creatinine that is thought to be a hemodynamic change rather than a direct nephrotoxic effect because no change in protein to creatinine ration and no abnormal urine analysis was present. No effect was observed on blood pressure. There was an increase in the glucose disposal rate.

Phase 2 Efficacy studies have demonstrated benefits. In patients with dyslipidemia, monotherapy with 300 – 900 mg significantly lowered LDL-C compared to placebo in three Phase 2 studies. In patients with baseline TG \geq 200 mg/dL (Study 1027-04), gemcabene lowered TG by 39% at the 300 mg dose compared with 5% lowering by placebo.

Human safety data is drawn from this collection of 19 clinical studies. The most frequent reported adverse events in healthy volunteers for single doses were headache, asthenia, nausea, dizziness and somnolence. The most frequent adverse events for 4 weeks were headache, infection, nausea, asthenia, photosensitivity reaction, rhinitis, diarrhea, flatulence, dizziness and pharyngitis. In patients with dyslipidemia treated for 8 weeks, headache, asthenia, dizziness and pain were more frequent with gemcabene compared to placebo at doses from 300-900 mg. Nausea, dyspepsia and flatulence were more frequent with gemcabene compared to placebo. In 1272 healthy adult volunteers and patients, only 17 discontinued due to gemcabene related adverse events. There were no treatment related serious adverse events and no deaths.

Important Literature and Data Relevant to the Trial

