6.1.2 DOSING AND ADMINISTRATION

The dose is 300 mg orally once a day.

The first dose of study drug will be administered at the research site on Study Day 1. On days with a scheduled office visit with blood sample collection, subject will remain fasted and should not take gemcabene until after the blood samples are collected at the site. On all other days, the subject will self-dose: taking study drug at the same time in the morning with a full glass (8 ounces) of water either with or without food. If a subject misses a dose prior to 6:00 PM, then the subject should take their dose. However, if past 6:00 PM, the subject should not dose and then count the dose as a “missed dose.” The subject will resume normal dosing the next day (i.e., do not take two doses the following day).

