8.3 ADVERSE EVENTS AND SERIOUS ADVERSE EVENTS

8.3.1 DEFINITION OF ADVERSE EVENTS (AE)

Adverse event means any untoward medical occurrence associated with the use of an intervention in humans, whether or not considered intervention-related (21 CFR 312.32 (a)).

An adverse event is defined as any untoward medical occurrence in a clinical investigation subject administered a pharmaceutical product, which does not necessarily have a causal relationship with this treatment. An adverse event can therefore be any unfavorable and/or unintended sign (including an abnormal laboratory finding), symptom, or disease temporally associated with the use of an investigational medicinal product, whether or not related to the investigational medicinal product. All adverse events, including observed or volunteered problems, complaints, or symptoms, are to be recorded on the appropriate eCRF.

Adverse events, which include abnormal and clinically significant clinical laboratory test variables, will be monitored and documented from the time of first dose of study drug (Study Day 1) until study participation is complete (the Follow-up Visit). Subjects should be instructed to report any adverse event that they experience to the Investigator. Beginning with the signing of the informed consent until the time of the first dose of study drug (Study Day 1), Investigators should make updates to medical history and record any pre-existing medical condition or signs or symptoms that changes in severity, frequency,

or seriousness in the medical history. Serious adverse events that occur prior to the first dose of study drug (Study Day 1) should be reported as an update to medical history as well as be reported on the appropriate adverse event eCRF. Beginning with the first dose of study drug (Study Day 1), Investigators should make an assessment for adverse events at each visit and record all adverse events, non-serious and serious, on the appropriate adverse event eCRF.

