14.1 PART 2: DE NOVO LIPOGENESIS

Study Subjects: 10 adolescents (as described above)

Study Design: Hepatic de novo lipogenesis will be measured in the fasting state (0 HR) and during the fructose enriched meal challenge (0, 2, 4 and 6 HRS) before Gemcabene treatment begins (Week 0) and after treatment is complete (Week 12).

Sample Collection and Processing:

- (1) VLDL (Sf20-400) particles will be isolated from 1 mL of plasma at the Biomarker Core Laboratory, split in two equal VLDL aliquots (one primary and one back-up sample), frozen at -80 °C and shipped to Metabolic Solutions, Inc. for triglyceride isolation and deuterium enrichment of VLDL-TG palmitate by IRMS.
- (2) Plasma (250 µL) will be collected at 0, 2, 4 and 6 HRS and frozen at -20 °C for body water enrichment analyses (Metabolic Solutions, Inc.). Spray-dried K2 EDTA vacutainers will be used to collect plasma for body water enrichment analyses.
- (3) VLDL-TG palmitate concentration

Data Analysis: Deuterium enrichment in VLDL-TG palmitate and plasma water will be determined by IRMS. Fractional DNL will be calculated from body water and VLDL-TG-palmitate deuterium enrichment using precursor-product relationships. Absolute DNL will be calculated as Fractional DNL x VLDL-TG palmitate pool size.

Endpoints:

Primary Endpoint:

- Fractional hepatic DNL in the fasting state (0 HR) and during meal stimulation (2 HR, 4 HR, 6 HR)

Secondary Endpoint:

- Absolute hepatic DNL in the fasting state (0 HR) and during meal stimulation (2 HR, 4 HR, 6 HR)

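### Table 1's two-sided Baseline window lets the Baseline MRI, ECG and questionnaires fall up to two days after the first dose, and it conflicts with Tables 2 and 3 and Appendix A

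*Combined protocol and SAP*

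**What the plan says.** Table 1 (section 1.3) heads the whole Baseline column "Baseline (Day 1 +/- 2 days". No footnote limits the window to the days before dosing. The column holds the second eligibility review, physical exam, MRI, ECG, PROMIS, diet, beverage and activity questionnaires, pregnancy test, blood draw, both sub-study procedures and the first drug dispensing.

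Section 6.1.2 ties Day 1 to treatment: "The first dose of study drug will be administered at the research site on Study Day 1". Section 8.3.1 does the same, collecting adverse events "from the time of first dose of study drug (Study Day 1" onwards. Section 6.1.2 also holds the dose on visit days until blood has been drawn. That rule covers blood samples only.

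Tables 2 and 3 label the same visit "Baseline (Day 1", closing the bracket there with no window. Appendix A, section 14.1, places the lipogenesis measurement "before Gemcabene treatment begins (Week 0", and section 14.2 says the same for cholesterol synthesis.

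The pregnancy-test row of Table 1 reads "Local Urine Pregnancy Test (WOCBP) | | X | X | X | X | | X | X | X | X". The first cell, Screening, is blank, so Baseline is the first scheduled test. Exclusion criterion 10 (section 5.2) rules out any girl with a positive pregnancy screen.

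**The concern.** If Day 1 is the first dose, a window reaching two days beyond it admits assessments made on treatment and labels them Baseline. Every change score in this trial is measured against Baseline without a control arm, so a reference taken on drug cannot be corrected by comparison with another group. The MRI is the most exposed outcome measure: hepatic steatosis is in the primary objective and in the study hypothesis, and the plan schedules no earlier scan. The ECG is scheduled only at Baseline and Week 2, so a late Baseline tracing leaves no scheduled pre-drug ECG.

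The window also sets parts of the protocol against each other. Staff working from Table 1 could be within window and still break the timing in Appendix A or Table 2. The pregnancy test and eligibility review sit under the same two-sided header, for a drug whose background section reports "Developmental toxicity studies demonstrated abnormalities and teratogenicity at doses >10 mg/kg/day in rats".

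**Working it through.** The plan gives no figure to reproduce here. The check is day arithmetic and a comparison of passages.

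**Day arithmetic**
- First dose: Day 1 (sections 6.1.2 and 8.3.1). Dosing is once daily.
- Late edge of the window: Day 1 + 2 = Day 3.
- Doses taken before a Day 3 assessment: Days 1 and 2, so 2; or 3 if the assessment follows the Day 3 dose.
- Length of treatment: Week 12 is Day 85, and 85 − 1 = 84 days.
- Share of the course: 2/84 = 2.4%; 3/84 = 3.6%.

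**What protects each Baseline item**

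| Baseline item | Scheduled at Screening too? | Text placing it before dose 1 |
|---|---|---|
| MRI | No | None |
| ECG | No | None |
| PROMIS, diet, beverage and activity questionnaires | No | None |
| Blood, including central ALT | Local chemistry only | Day 1 label in Tables 2 and 3, plus the dose-after-draw rule in 6.1.2 |
| Lipogenesis, cholesterol synthesis | No | Explicit in Appendix A, 14.1 and 14.2 |
| Postprandial lipids | No | Indirect: Appendix A, 12.1 runs both sub-studies simultaneously in the same 10 participants |
| Pregnancy test | No | Implied by exclusion 10 and the Baseline eligibility review; not stated |
| Eligibility review | Yes | Implied by its purpose; not stated for the Baseline review |

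The first three rows have no protection. The next three are protected by text that disagrees with the Table 1 header. The last two rest on inference.

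**What depends on the MRI.** By sections 3 and 8.1, the Baseline scan supplies the reference for hepatic and pancreatic fat (HepaFat), for LIF and cT1 (Liver MultiScan), and for body composition (AMRA). The scan allowed as diagnostic evidence under inclusion criterion 5c may be up to three years old and is not a trial baseline.

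**Blood.** Read with Table 2, blood is drawn on Day 1 and the dose follows, so it is pre-dose. Only if Table 1's window were applied to the blood-draw row instead would the hold rule fall short: on Day 3 it would withhold that day's dose but not the two already taken.

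**The case against.** The strongest reply is that the window moves the whole visit. Dispensing sits in the same column, so the visit and the first dose would shift together and nothing would follow dosing. But the first dose itself defines Day 1, so a visit that always carries the first dose is always Day 1, and a window around Day 1 would have nothing to vary against. The amendment history (section 10.4, Version 2.0) gives ease of scheduling the MRI and other visit activities as the reason for the window. That suggests activities done on a different day from dosing, and the current table still carries the window. What stands is that sites may well complete everything before dosing in practice; the text does not require it.

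A second reply is that two days hardly matter when the Week 12 visit itself has a window of 10 days either way. On size, that is fair.

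Three stronger readings are tempting, and the documents do not support them:
- *The lipogenesis sub-study would be diluted.* A reader might infer this from the mechanism: "Gemcabene may reduce ACC1 mRNA expression as well as inhibit ACC1 enzymatic activity". But Appendix A requires these measurements before treatment begins, and the documents give no onset time for any inhibition, so no dilution can be sized. The defect there is a conflict between Table 1 and Appendix A.
- *Every efficacy endpoint, including ALT, is compromised.* Baseline ALT and the other blood measures are largely protected by the Day 1 label and the dose-after-draw rule.
- *Pregnancy and eligibility are checked after exposure.* That would require a site to give the drug and review the exclusion criteria afterwards. Exclusion 10, and the statement in section 2.3.1 that pregnant women should not receive gemcabene, imply the opposite order. The gap is that the order is not written down.

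**Conclusion.** The point holds for the MRI, ECG and questionnaires: as written, they can follow up to two doses, or three if the MRI comes after the Day 3 dose. For the sub-study and blood it is an inconsistency between Table 1 and the more specific text. For the pregnancy test and eligibility review it is an unstated sequence.

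The bias in MRI change is probably small. The exposure at stake is 2.4% to 3.6% of the course. That is a share of doses, not an estimate of lost effect; the documents give no time course for liver fat, so the effect cannot be sized. The direction is clearer: if the drug works, a late Baseline understates the change. The conclusion rests on Day 1 being the dosing day, as sections 6.1.2 and 8.3.1 say, and on the Table 1 window applying to the whole column, as its header says. This is a cheap improvement; it does not threaten the primary analysis.

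**What to change.** - In Table 1, make the Baseline window for the MRI, ECG, questionnaires and other outcome measures one-sided: Day −2 to Day 1, completed before the first dose, with Day −1 meaning the day before Day 1. State that the first dose defines Day 1.
- Reconcile Table 1 with Tables 2 and 3, section 6.1.2, exclusion criterion 10 and Appendix A, so that the documents agree and state which Baseline procedures precede the first dose. For the pregnancy test and eligibility review, this asks the sponsor to write down the sequence that its own criteria imply; it proposes no new clinical rule.

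The cost is a changed column header and a sentence or footnote. The one practical downside is that if the MRI slot slips, the start of treatment slips with it. Sample size and analysis are unaffected.
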